7.4.2. Randomization

Randomization is to occur only after verification of all inclusion/exclusion criteria. Once the subject has signed the Institutional Review Board (IRB)/Ethics Committee (EC)-approved study ICF and has met all general inclusion and none of the exclusion criteria, the subject will be eligible for randomization. Randomization schedules will be computer-generated in advance, using a pseudo-random number generator and loaded into the EDC system. Randomization assignments will be obtained from the EDC system at the time of procedure. Randomization will be stratified by clinical site. Within each site, eligible subjects will be randomized in a 1:1 ratio to receive each treatment method.

For back-up randomization, sites will be instructed to randomize subjects via back-up envelopes only in cases of unsuccessful EDC access. Envelopes are sequentially numbered sealed opaque envelopes containing randomized treatments.

7.4.3. Treatment – *Office Visit*

- Cholangiogram or other Common Bile Duct Imaging (prior to stent placement)
- Stent Placement Procedure
NOTE: For subjects randomized to PS, at least two 8.5 or 10 Fr. PS should be placed whenever possible
- Adverse Event/Device Malfunction Assessment

7.4.4. Post-Stent Placement Follow-Up (Month 1) – *Office or Telephone Visit*

- Liver Function Tests
- Assessment of Biliary Obstructive Symptoms (See Section 7.4.1)
- Adverse Event/Device Malfunction Assessment

7.4.5. Plastic Stent Exchange (Month 4 and 8 – PS Only) – *Office Visit*

- Plastic Stent Exchange
- Adverse Event/Device Malfunction Assessment
- If subject is not re-stented after this visit, Liver Function Tests must be drawn.

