Follow-Up Schedule	
 • Baseline: Subject screening, enrollment, LFTs and symptoms. • Study Treatment Procedure: 
 ○ Group A (MS): Stent Placement ○ Group B (PS): Stent Placement: Two or more 8.5 Fr. or 10 Fr. PS whenever possible • 1 Month Follow-up: 
 ○ Group A (MS): LFTs and symptoms ○ Group B (PS): LFTs and symptoms • Stent Exchange Follow-up: 
 ○ Group A (MS): None ○ Group B (PS): Month 4 and Month 8 • Stent Removal: 
 ○ Group A (MS): Removal at Month 12, LFTs and symptoms ○ Group B (PS): Removal of last stents at Month 12, LFTs and symptoms • Post-Stent Removal Follow-Up 
 ○ Group A (MS): Month 24 – LFTs and symptoms ○ Group B (PS): Month 24 – LFTs and symptoms • Additional ERCP visits as needed 
Note: Recurrent strictures will be treated with a metal stent in Group A (MS) and with plastic stents in Group B (PS) – no cross-over. Re-stenting after the per-protocol 12 month stenting period will be considered primary endpoint failures. Follow-up, however, will continue until Month 24 after initial stent placement for all subjects, in order to assess all secondary endpoints in a comparative fashion for the

	MS and PS arms.
Key Inclusion Criteria	
 • Age 18 or older • Willing and able to comply with the study procedures and provide written informed consent to participate in the study • Chronic pancreatitis • Symptomatic bile duct stricture (defined by cholangitis or persistent jaundice for at least one month or cholestasis associated with at least 3 times normal alkaline phosphatase levels) documented at time of enrollment for naïve stricture or at the time of prior plastic stent placement in strictures that had one prior plastic stent inserted.¹² • Common bile duct stricture based on imaging assessment of dilatation of the common and/or intrahepatic bile ducts

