The schedule of observations and assessments to take place during the study follows on the next page.

Table 1. Study Event Schedule

Study Visit	Screening/ Baseline	Treatment	Mo. 1* (30 d)	Mo. 4 (120 d)	Mo. 8 (240 d)	Mo. 11-12 (330-360 d)	Mo 24* (720 d)	Additional ERCP
Window	≤ 5 days prior to treatment	N/A	±10 d	±30 d	±30 d	See range above	±30 d	NA
ICF	X							
Eligibility Assessment	X							
Demographics	X							
Medical History	X							
Liver Function Normal Ranges	X**						X	X****
Liver Function Tests	X		X	***	***	X	X	X
Assessment of Biliary Obstructive Symptoms	X		X			X	X	X****
Randomization		X						
Stent Placement/Exchange		X		PS Only	PS Only			X (if done)
Stent Removal						X		
Cholangiogram or other Common Bile Duct Imaging	X (prior to stent placement)					X (after stent removal)		X (if standard of practice)
AE/Device Malfunction Assessment	Report as occurs/needed per the Protocol Reporting Requirements – See Section 11.							
Protocol Deviations	Report as occurs/needed.							

*Visit may be conducted in the office or via telephone with liver function tests drawn and sent from local clinic/hospital.

**In addition to baseline LFTs, LFTs are also to be collected from time of original plastic stent placement for any subject with a prior plastic stent.

***If subject is not re-stented after Month 4 or 8 Plastic Stent Exchange, Liver Function Tests must be collected at that visit.

****Required for any visit that results in re-stenting

7.2. *Study Candidate Screening*

No study-specific testing will be conducted until after the subject has signed an ICF. A Screen Failure/Enrolled Log will be maintained in EDC by the center to document select information about candidates who signed consent.

7.3. *Informed Consent*

Written Informed Consent must be obtained for all subjects who are potential study candidates. Subjects will be asked to sign the Informed Consent form before any study-specific tests or procedures are performed. The Informed Consent form is study-specific and must be approved by the study Institutional Review Board (IRB)/Ethics Committee (EC). Study personnel should explain that even if a subject agrees to participate in the study and signs the ICF, the ERCP procedure may demonstrate that the subject is not a suitable candidate for the study.

7.4. *Study Visits*

7.4.1. **Screening/Baseline – Visits/Assessments must occur within 5 days prior to stent placement – Office Visit**

- Informed Consent (See Section 7.3)

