Serious Adverse Device Effect (SADE) Ref: ISO 14155-2011	An adverse device effect that has resulted in any of the consequences characteristic of a serious adverse event. 
Note: All SAEs that could have led to a SADE if suitable action had not been taken or if circumstances had been less fortunate shall be reported as required by the local IRB/EC, national regulations, or the protocol. If applicable, see MEDDEV 2.7/3 12/2010 for reporting timeline requirements.

Device Deficiency Ref: ISO 14155-2011 Ref: MEDDEV 2.7/3 12/2010	A device deficiency is any inadequacy of a medical device with respect to its identity, quality, durability, reliability, safety or performance. 
Note: Device deficiencies include malfunctions, use errors, and inadequate labeling.
 
Note: All device deficiencies that could have led to a SADE if suitable action had not been taken or if circumstances had been less fortunate shall be reported as required by the local IRB/EC, national regulations, or the

Table 11.1-1: Adverse Event Definitions

Term	Definition
	protocol. If applicable, see MEDDEV 2.7/3 12/2010 for reporting timeline requirements.

Abbreviations: EC=Ethics Committee; IRB=Institutional Review Board

Underlying diseases are not reported as AEs unless there is an increase in severity or frequency during the course of the investigation. Death should not be recorded as an AE, but should only be reflected as an outcome of a specific SAE (see Table 11.1-1 for AE definitions).

Any AE experienced by the study subject after informed consent, whether during or subsequent to the procedure, must be recorded in the eCRF.

Refer to Section 10.1 for the known risks associated with the study device(s).

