7.3 Rules and Definitions

Binary event rates (proportions) will be reported on a per patient basis.

The last follow-up date will be the latest of the following dates for each patient: date of an adverse event, index procedure date, follow-up visit date, any stent or ECRP procedure date, stent removal date, and device event date.

Stricture resolution at 24 months is defined by the following two criteria being met:

• Absence of re-stenting after the per-protocol stenting period through the 24 month visit

Version AA March 20, 2013 Boston Scientific WallFlex Biliary FC CP RCT SAP 90913894/Ver. AA Page 12 of 13 • Absence of cholestasis at the 24 month visit, defined as alkaline phosphatase level not exceeding 2 times the level at completion of the per-protocol stenting period

Primary endpoint failures are 1) subjects who are re-stented during follow-up after the per-protocol stenting period and 2) subjects who have not been re-stented at month 24 but have alkaline phosphatase level exceeding 2 times the level at completion of the per-protocol stenting period.

Subjects who experience early stent removal or complete distal stent migration without subsequent re-stenting will not be considered failures. If re-stenting occurs, but the cumulative stenting period does not exceed 12 months, the subject remains eligible for primary endpoint assessment.

For the final tables, two-sided exact tests will be done to test for differences between the two groups for removability and AEs. A one-sided non-inferiority Farrington-Manning test will be done to see if stricture resolution is non-inferior in the Metal group compared to the Plastic group. A two-sided student's t-test will done to test for differences between the two groups for the number of ERCP procedures done.

Version AA March 20, 2013 Boston Scientific WallFlex Biliary FC CP RCT SAP 90913894/Ver. AA Page 13 of 13

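### Scheduled adverse-event questioning after the procedure is unequal (five assessments for plastic, three for metal), so mild related events in the metal arm may be under-recorded

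*Protocol*

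**What the plan says.** **Visits.** The heading of Protocol 7.4.5 begins "Plastic Stent Exchange (Month 4 and 8" and restricts the visit to the plastic arm; the section lists an "Adverse Event/Device Malfunction Assessment". The same line appears for both arms at baseline (7.4.1), treatment (7.4.3), month 1 (7.4.4), removal at month 12 (7.4.6), month 24 (7.4.7) and any additional ERCP (7.4.8). Under stent-exchange follow-up, the synopsis gives "Group A (MS): None". Table 1 sets the removal visit at "Mo. 11-12 (330-360 d").

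**Reporting between visits.** The adverse-event row of Table 1 is not tied to visits: "Report as occurs/needed per the Protocol Reporting Requirements". Protocol 11.1 adds: "Any AE experienced by the study subject after informed consent, whether during or subsequent to the procedure, must be recorded in the eCRF". Section 11.3 starts the reporting clocks (2 business days for serious events, 10 for device- or procedure-related events) when the site becomes aware of the event.

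**Analysis.** Complication rates are part of the objective in Protocol section 3. Related adverse events are the first secondary endpoint (4.2). SAP 7.3 reports binary rates per patient and states that "two-sided exact tests will be done to test for differences between the two groups for removability and AEs". The study is not blinded (Protocol section 5). Neither document mentions the unequal contact or plans an analysis for it.

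**The concern.** A between-arm comparison of adverse events is fair only if the events have a similar chance of being found in each arm. Plastic subjects return to the site twice during stenting, and the protocol lists an adverse-event assessment each time. Over the same months nothing is scheduled for metal subjects. Continuous reporting applies to both arms, but a site can report only what it knows.

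At stake is a secondary endpoint that is also named in the primary objective. A mild related event that resolves at home, and that the subject does not recall at month 12, lowers the recorded metal rate. If that happens, the error favours metal. The non-inferiority test of stricture resolution is not affected.

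**Working it through.** **1. Scheduled assessments after the procedure (Protocol 7.4.4 to 7.4.7)**

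| | Month 1 | Month 4 | Month 8 | Month 12 | Month 24 | Total |
|---|---|---|---|---|---|---|
| Plastic | yes | yes | yes | yes | yes | 5 |
| Metal | yes | no | no | yes | yes | 3 |

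Counting baseline and treatment, the totals are 7 and 5.

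**2. Longest gap during stenting (days in Table 1)**

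- Metal, nominal: 330 − 30 = 300 to 360 − 30 = 330 days. With the ±10-day window at month 1: 330 − 40 = 290 to 360 − 20 = 340 days.
- Plastic, nominal: 120 − 30 = 90, 240 − 120 = 120, and 330 − 240 = 90 to 360 − 240 = 120. The longest is 120 days.

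**3. Illustrative effect on the test**

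The plan states no adverse-event rate, detection rate or power for this comparison, so there is no figure of its own to reproduce. The arm size of 82 comes from SAP 3.1.2 (74 × 1.10 = 81.4, taken as 82).

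Assumptions:
- The true per-patient rate of related events, p, is the same in both arms, at 20% or 30%.
- The exact test is Fisher's two-sided test at 5%. SAP 7.3 names neither the test nor its level.
- All 82 subjects per arm are analysed.
- A fraction m of metal subjects with a related event have none recorded. No plastic subject is missed.

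Only a subject whose sole related events are non-serious and fall in the gap can be lost. So m = g × u, where g is the share of affected metal subjects who are in that position and u is the share of those who are missed. With g = 50% and u = 20-40%, m = 0.5 × 0.2 = 10% to 0.5 × 0.4 = 20%.

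The recorded metal rate is p × (1 − m). The rejection probability is the sum, over all pairs of counts for which Fisher's p-value is below 0.05, of the product of the two binomial probabilities.

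| True rate p | Missed m | Recorded metal rate | Difference | Test rejects | Of which favouring metal |
|---|---|---|---|---|---|
| 30% | 0 | 30% | 0 | 3.4% | 1.7% |
| 30% | 10% | 27% | 3 points | 5.0% | 4.4% |
| 30% | 20% | 24% | 6 points | 10.4% | 10.2% |
| 20% | 0 | 20% | 0 | 3.1% | 1.5% |
| 20% | 10% | 18% | 2 points | 3.9% | 3.3% |
| 20% | 20% | 16% | 4 points | 6.8% | 6.6% |

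The test is conservative when nothing is missed, so the comparison is with 3.4% and 3.1%, not 5%. Nearly all of the excess rejections favour metal.

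**The case against.** The case against any practical bias is substantial.

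- **Later visits look back.** Every metal subject is due at the removal visit, with an adverse-event assessment, symptom assessment, liver tests and imaging, and again at month 24. SAP 3.1.3 has rules for incomplete onset dates. A reader might infer that events in the gap are recorded only if the subject or another hospital reports them unprompted. The documents do not support that.
- **Most defined complications bring the patient to care.** Under the definitions in Protocol 10.1, pancreatitis involves more than one night in hospital, cholangitis an intervention, occlusion a stent replacement, bleeding endoscopic haemostasis or transfusion, and cholecystitis emergency surgery.
- **The itemised symptom list is scheduled equally.** It is due at baseline and months 1, 12 and 24 in both arms, and is not listed at the plastic exchanges.
- **Rates are per patient.** A missed event changes nothing if the subject has another recorded event.
- **Exchange procedures cause real events.** A reader might take extra plastic-arm events at months 4 and 8 for detection bias. Events caused by the exchanges are a genuine cost of that strategy.

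All of this stands and limits the risk to mild, non-serious related events in the gap. It does not remove the risk. Recall at month 12 of a minor event up to about ten months old is weaker than a question at the time, and as-occurs reporting still depends on the site's awareness.

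**Conclusion.** The point holds as one of unequal solicitation: five scheduled assessments against three, and a longest nominal gap of 300-330 days against 120. Mild related events in the metal arm may be under-ascertained, and any such loss would favour metal.

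A reader might infer that the complication comparison is biased, and by a large amount. The documents do not show that it is biased, and they give nothing from which to size it. Applying a 20-40% loss to the whole 24-month metal rate would put rejection at 10.4-36.9% for a true rate of 30%, and 6.8-21.9% for 20%. But placement, month 1, removal and months 12-24 are assessed equally in both arms. With half of affected subjects exposed to loss, a 40% overall loss would need 0.40 / 0.50 = 80% of them to be missed. The 10-20% range is more restrained, but it is still an assumption. It gives 5.0-10.4% against 3.4%, or 3.9-6.8% against 3.1%.

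This is worth correcting because the outcome is in the primary objective, the remedy is cheap, and unrecorded mild events cannot be reliably reconstructed later.

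**What to change.** **Protocol 7.4.5 and Table 1:** add a telephone contact for the metal arm at months 4 and 8, limited to adverse events and using the same questions as the plastic visit. Telephone visits are already accepted at months 1 and 24. This makes the count five in each arm and brings the longest nominal metal gap down to 120 days. The cost is 2 × 82 = 164 short calls by existing staff and a minor amendment. Treatment, the primary endpoint and the sample size do not change.

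**SAP 7.3:** add a between-arm comparison restricted to serious related adverse events, as a check that depends less on visit frequency. It needs no new data. The comparison of all related events stays, and events caused by the exchange procedures continue to count for the plastic arm.

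**While amending:** Protocol 11.1 requires every adverse event to be recorded, whereas 11.3.2 says that unrelated ones are not collected. This applies equally to both arms, but the two sections must be reconciled so that sites ask for and record the same events.

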7.4.6. Primary Stent Removal Visit (Month 12) – *Office Visit*

- Stent Removal Procedure
- Cholangiogram or other Common Bile Duct Imaging (post-stent removal)
- Liver Function Tests
- Assessment of Biliary Obstructive Symptoms
- Adverse Event/Device Malfunction Assessment

7.4.7. Post-Stent Removal Follow-Up (Months 24) – *Office or Telephone Visit*

- Assessment of Biliary Obstructive Symptoms
- Collection of Liver Function Normal Ranges
- Liver Function Tests
- Adverse Event/Device Malfunction Assessment

7.4.8. Additional ERCP

- Liver Function Tests
- Collection of Liver Function Normal Ranges (required for any visit that results in re-stenting)
- Assessment of Biliary Obstructive Symptoms (required for any visit that results in re-stenting)
- Cholangiogram or other Common Bile Duct Imaging (only to be collected in database if standard of care per institution)
- Adverse Event/Device Malfunction Assessment

NOTE: Recurrent strictures must be treated with a metal stent in Group A (MS) and with plastic stents in Group B (PS) – no cross-over.

7.5. Study Completion

Each subject will be followed for 2 years post-initial stent placement. Recurrent strictures will be treated with a metal stent in Group A (MS) and with plastic stents in Group B (PS) – no cross-over. Follow-up will continue until Month 24 after initial stent placement for all subjects, in order to assess all secondary endpoints in a comparative fashion for the MS and PS arms.

Additional visits may be conducted at the Investigator’s discretion in accordance with Adverse Event or Device Malfunction data collection. A subject will be considered lost to follow-up if the subject remains unresponsive to communication after three documented attempts by study staff.

7.6. Source Documents

The Investigator/institution guarantees direct access to original source documents, including cholangiogram and/or imaging documentation, by BSC personnel, their designees, and appropriate regulatory authorities. In the event that the original medical records cannot be obtained for a subject that is seen by a non-study physician at a non-study institution, photocopies of the original source documents must be made available for review.

8. Statistical Considerations

8.1. Objective

Rate of Stricture Resolution in the Metal Stent group is non-inferior to the Plastic Stent group.

Statistical testing will be performed to determine if the rate of stricture resolution for the metal stent is non-inferior to the plastic stent group. The null hypothesis is that the rate of stricture resolution is non-inferior in the Metal Stent Arm versus the Plastic Stent Arm:

$H_0: \pi_{test} - \pi_{control} \geq \Delta$ (Inferior)

$H_a: \pi_{test} - \pi_{control} < \Delta$ (Non-inferior)

February 15, 2013

FINAL

where π_{test} and $\pi_{control}$ are the probabilities of having a stricture resolution in the metal stent arm and the plastic stent arm respectively, and Δ is defined as the non-inferiority margin.

The sample size was calculated for a one-sided 0.050 Farrington-Manning test using SAS 9.2®. If the P value from the Farrington-Manning test is <0.05 then the metal stent group will be considered non-inferior to the plastic stent group. The expected probability of a stricture resolution in the metal stent arm and plastic stent arm is 66.0%, which was taken from the 95% CIs from the meta-analysis below. The non-inferiority margin (Δ) is 20%. Given these assumptions, and a one-sided 5% significance level, $2 \times 74 = 148$ subjects will provide 80% power to reject the null hypothesis, that the metal stent group is inferior to the plastic stent group. To compensate for possible loss of subjects between randomization and complete assessment of inclusion/exclusion criteria, an additional 10% of subjects will be enrolled for a total of $2 \times 82 = 164$.

8.2. *Justification for Study Design and Sample Size Calculations*

- A literature search of metal and or plastic stenting for treatment of benign biliary strictures secondary to chronic pancreatitis yielded 4 articles representing 70 subjects treated with metal stenting (MS)²⁻⁷ and 3 articles representing 60 subjects treated with plastic stenting (PS)⁸⁻¹³.
- The following meta-analysis was conducted of the probability of stricture resolution:
 - Metal Stenting: A meta-analysis of the stricture resolution rate during the reported follow-up after initial stent placement yields a proportion of 0.762 [95% CI: 0.593 – 0.895]²⁻⁷.
 - Plastic Stenting: A meta-analysis of the stricture resolution rate during the reported follow-up after initial stent placement yields a proportion of 0.611 [95% CI: 0.311 – 0.870]⁸⁻¹³.

We wish to demonstrate that the rate of stricture resolution using the metal stent approach is non-inferior compared to the plastic stent approach.

8.3. *Eligibility of Subjects, Exclusions, and Missing Data*

Handling of dropouts and missing data will depend on their frequency and the nature of the outcome measure and will be analyzed per the SAP (Statistical Analysis Plan).

8.4. *Analysis Populations*

8.4.1. **Enrolled Cohort**

A subject is considered “enrolled” after signing the study-specific ICF. Subjects who sign the ICF but subsequently do not meet one or more of the selection criteria will be considered screen failures and excluded from the study.

8.4.2. Intent-to-Treat Cohort

This cohort consists of those “enrolled” subjects who meet all inclusion/exclusion criteria and are subsequently randomized. Subjects in this cohort who do not receive a study stent(s) will be counted towards the enrollment ceiling. Any adverse events occurring or resulting from a treatment attempt will be collected. Protocol deviations will be collected as necessary.

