The sample size was calculated for a one-sided 0.050 Farrington-Manning test using SAS 9.2®. If the P value from the Farrington-Manning test is <0.05 then the metal stent group will be considered non-inferior to the plastic stent group. The expected probability of stricture resolution in the metal stent arm and plastic stent arm is 66.0%, which was taken from the 95% CIs from the meta-analysis above. The non-inferiority margin (Δ) is 20%. Given these assumptions and a one-sided 5% significance level, $2 \times 74 = 148$ subjects will provide 80% power to reject the null hypothesis, that the metal stent group is inferior to the plastic stent group. To compensate for possible loss of subjects after enrollment and complete assessment of inclusion/exclusion criteria, an additional 10% of subjects will be enrolled, for a total of $2 \times 82 = 164$.

Table of Contents

1. Introduction	10
1.1. Introduction	10
1.2. Plastic Stents in Chronic Pancreatitis Strictures	10
1.3. Metal Stents in Chronic Pancreatitis Strictures.....	11
2. Device Description	11
3. Primary Objectives.....	12
4. Endpoints.....	12
4.1. Primary Endpoint	12
4.2. Secondary Endpoints.....	13
5. Design.....	14
5.1. Inclusion Criteria:.....	14
5.2. Exclusion Criteria:	14
6. Subject Accountability	15
6.1. Point of Enrollment	15
6.2. Withdrawal.....	15
7. Study Methods	15
7.1. Data Collection	15
7.2. Study Candidate Screening	17
7.3. Informed Consent.....	17
7.4. Study Visits	17
7.5. Study Completion	19
7.6. Source Documents	19
8. Statistical Considerations	19
8.1. Objective	19
8.2. Justification for Study Design and Sample Size Calculations	20
8.3. Eligibility of Subjects, Exclusions, and Missing Data.....	20
8.4. Analysis Populations.....	20
8.5. Analysis.....	21
8.6. Statistical Analysis.....	21
9. Data Management	22
9.1. Data Collection, Processing, and Review	22
9.2. Data Retention.....	22
10. Potential Risks and Benefits	22
10.1. Anticipated Adverse Device Effects	22
10.2. Risk Minimization Actions	24
10.3. Anticipated Benefits.....	24
10.4. Risk to Benefit Rationale	24
11. Safety Reporting	24
11.1. Definitions and Classification.....	24
11.2. Relationship to Study Device(s)	26
11.3. Investigator Reporting Requirements	27

11.4. Boston Scientific Device Deficiencies.....27
11.5. Reporting to Regulatory Authorities / IRBs / ECs / Investigators.....27
12. Amendments27
13. Deviations28
14. Device/Equipment Accountability28
15. Compliance.....28

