3.1.2 Sample Size

A literature search of metal and or plastic stenting for treatment of benign biliary strictures secondary to chronic pancreatitis yielded 4 articles representing 70 subjects treated with metal stenting (MS)²⁻⁷ and 3 articles representing 60 subjects treated with plastic stenting (PS)⁸⁻¹³.

The following meta-analysis was conducted of the probability of stricture resolution:

- Metal Stenting: A meta-analysis of the stricture resolution rate during the reported follow-up after initial stent placement yields a proportion of 0.762 [95% CI: 0.593 0.895]²⁻⁷.
- Plastic Stenting: A meta-analysis of the stricture resolution rate during the reported follow-up after initial stent placement yields a proportion of 0.611 [95% CI: 0.311 0.870] ⁸⁻¹³.

The sample size was calculated for a one-sided 0.050 Farrington-Manning test using SAS 9.2®. If the P value from the Farrington-Manning test is <0.05 then the metal stent group will be considered non-inferior to the plastic stent group. The expected probability of a stricture resolution in the metal stent arm and plastic stent arm is 66.0%, which was taken from the 95% CIs from the meta-analysis above. The non-inferiority margin (Δ) is 20%. Given these assumptions, and a one-sided 5% significance level, 2 x 74 = 148 subjects will provide 80% power to reject the null hypothesis, that the metal stent group is inferior to the plastic stent group. To compensate for possible loss of subjects between enrollment and complete assessment of inclusion/exclusion criteria and subsequent randomization, an additional 10% of subjects will be enrolled for a total of 2 x 82 = 164.

Version AA March 20, 2013 Boston Scientific WallFlex Biliary FC CP RCT SAP 90913894/Ver. AA Page 8 of 13

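### Protocol 8.1 allows for eligibility losses after randomisation, against Protocol 7.4.2 and SAP 3.1.2, and no rule keeps a randomised subject later found ineligible in the ITT cohort

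*Protocol*

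**What the plan says.** **Cohort definitions.** Protocol 8.4.2 and SAP 4.1 build the ITT cohort from enrolled "subjects who meet all inclusion/exclusion criteria and are subsequently randomized". Protocol 8.4.1, repeated in SAP 4.1, counts a subject as enrolled once consent is signed. It adds that consented subjects who later "do not meet one or more of the selection criteria will be considered screen failures and excluded from the study". The per-protocol cohort is the ITT subset that receives study stents without major deviations.

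**Timing of randomisation.** Protocol 7.4.2 states: "Randomization is to occur only after verification of all inclusion/exclusion criteria". It also states: "Randomization assignments will be obtained from the EDC system at the time of procedure".

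**Reason for the 10% allowance.** This is given in four places, with three wordings:
- Protocol 8.1: "possible loss of subjects between randomization and complete assessment of inclusion/exclusion criteria".
- Protocol synopsis and SAP section 1: "possible loss of subjects after enrollment and complete assessment of inclusion/exclusion criteria".
- SAP 3.1.2: loss "between enrollment and complete assessment of inclusion/exclusion criteria and subsequent randomization".

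**Context.** Protocol section 5 describes the study as non-blinded. Protocol 7.3 asks staff to tell candidates that the ERCP may show them to be unsuitable. Malignant stricture and investigator discretion are both exclusion criteria (Protocol 5.2).

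**The concern.** The protocol gives two incompatible answers on whether eligibility is complete when the assignment is drawn. Under 7.4.2 it is. Under the 8.1 allowance it is not, because subjects are lost after randomisation while eligibility is still being assessed.

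The cohort rules do not settle what happens to those subjects. Take a subject judged eligible, randomised, and later found not to have met a criterion, for example because the stricture proves to be malignant. That subject did not meet all criteria, so the literal ITT definition leaves them out. The screen-failure sentence could be applied to them too, since it runs from consent with no stated end point. Neither document says that they stay.

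In an open-label trial, someone who knows the arm, and perhaps the outcome, could then decide who counts. If those decisions were related to both arm and outcome, the cohort called ITT would lose the protection of randomisation and the non-inferiority test could be biased in either direction.

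**Working it through.** **1. The texts side by side**

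| Place | When eligibility loss occurs |
|---|---|
| Protocol 7.4.2 | Before randomisation (all criteria verified first) |
| SAP 3.1.2 | Between enrolment and randomisation |
| Protocol synopsis, SAP section 1 | After enrolment, meaning after consent; no reference to randomisation |
| Protocol 8.1 | After randomisation |

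Protocol 8.1 stands alone. It contradicts 7.4.2 and SAP 3.1.2 directly.

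**2. The plan's own sample size**

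Inputs (Protocol 8.1): 66% in both arms, margin 0.20, one-sided alpha 0.05, power 80%. With the null variance at 46% and 66%:

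n per arm = [1.645 × √(0.46×0.54 + 0.66×0.34) + 0.842 × √(2×0.66×0.34)]² / 0.20² = 71.8, so 72.

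The plan's 74 is within 2 per arm of this. Exact enumeration of the Farrington-Manning test gives 83.2% power at 74 per arm. The allowance is 74 × 1.10 = 81.4, rounded to 82, which is 8 extra per arm. The stated 148 and 164 are not in question, and defining ITT as all randomised subjects does not change them.

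**3. What removals could do**

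The documents give no number of removals. As an assumed range I use 0 to 8 in one arm, 8 being the size of the allowance.

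Method: exact binomial enumeration of the Farrington-Manning test (restricted maximum-likelihood variance, reject if z > 1.645), starting from 82 per arm. Removing k failures from an arm with rate p leaves n = 82 − k and rate 82p/(82 − k).

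For the metal arm at the margin (46% against 66% plastic), 82 × 0.46 = 37.72 expected resolutions. Removing 4 failures gives 37.72/78 = 48.4%; removing 8 gives 37.72/74 = 51.0%.

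For the plastic arm at 66%, 82 × 0.66 = 54.12. Removing 4 gives 54.12/78 = 69.4%; removing 8 gives 54.12/74 = 73.1%.

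| Removed subjects | Quantity | k = 0 | k = 4 | k = 8 |
|---|---|---|---|---|
| Metal failures only; true rates 46% and 66% | False non-inferiority | 5.7% | 9.5% | 16.2% |
| Plastic failures only; both arms 66% | Power | 86% | 73% | 54% |
| k failures from each arm; 46% and 66% | False non-inferiority | 5.7% | 3.6% | 3.0% |
| Metal subjects regardless of outcome; 46% and 66% | False non-inferiority | 5.7% | 5.2% | 5.1% |

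The 5.7% at k = 0 is the test's own exact error at these rates, so inflation is measured from there. Modelling the metal-only removal as a fixed count of failures, without rescaling the rate, gives 9.8% and 16.8% in place of 9.5% and 16.2%.

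The first two rows are extremes. Eight is 29% of the plastic failures expected at 66% (82 × 0.34 = 27.9), and 18% of the metal failures expected at 46% (82 × 0.54 = 44.3).

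**The case against.** The strongest reply is that the ITT definition puts eligibility first and randomisation second, exactly as Protocol 7.4.2 requires. Read together, the two make ITT everyone who was correctly randomised. Section 8.4.2 keeps randomised subjects who receive no stent, and major deviations lead to removal only at the per-protocol step. On this view the 8.1 clause is a slip that SAP 3.1.2 puts right.

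Much of that stands. A reader might infer that the plan expects eligibility losses after randomisation and will strip failures from the primary comparison. The documents do not support this, for these reasons:
- The expectation rests on one clause in Protocol 8.1, and SAP 3.1.2 points the opposite way.
- An arm-dependent search for ineligible subjects is not planned. Table 1 schedules the eligibility assessment at screening/baseline only, and the month 4 and 8 plastic-exchange visits (Protocol 7.4.5) contain no eligibility review. Investigator discretion is an entry criterion, to be cleared before randomisation.
- That ineligible subjects would mostly be failures is an assumption. Failure in Protocol 4.1.2 means re-stenting after the stenting period or a raised alkaline phosphatase at month 24. A subject with cancer may not reach month 24, and SAP 3.1.3 excludes insufficient follow-up from the rate however ITT is worded.
- SAP 4.1 lists three cohorts and names none as primary, so the documents do not tie the primary test to ITT alone.

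What the reply does not cover is the subject verified as eligible, randomised, and later found not to have been. The sentence on subjects without a stent concerns people already in the cohort, so it does not help. For this case the text is silent, and read literally it removes them.

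**Conclusion.** The point holds as a defect of wording that leaves an analysis decision open. Protocol 8.1 contradicts Protocol 7.4.2 and SAP 3.1.2 on whether eligibility is complete at randomisation, and no rule keeps a randomised subject later found ineligible in ITT.

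Its size cannot be fixed from the documents. The rise from 5.7% to 9.5% or 16.2% assumes that 4 or 8 subjects are removed, all failures, all from the metal arm, with true rates exactly at the margin. It is an upper illustration and not a forecast. Balanced removal of failures, or removal unrelated to outcome, does not inflate the error. Protocol 8.1's 8 per arm is an inflation allowance and should not be read as a prediction of one-sided exclusions. The matter is still worth settling before analysis, because otherwise an unblinded judgement decides who is counted.

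**What to change.** - **Protocol 8.4.2 and SAP 4.1:** define ITT as all randomised subjects, analysed in the arm assigned.
- **Protocol 8.4.1 and SAP 4.1:** limit screen failure to subjects found ineligible before the assignment is drawn.
- **Same sections:** treat ineligibility found later as a protocol deviation. The subject stays in ITT, and only per-protocol membership is affected.
- **Protocol 8.1:** reword the reason for the 10% allowance to agree with Protocol 7.4.2 and SAP 3.1.2, and align the synopsis and SAP section 1 with it.

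No new procedure or imaging requirement is needed, since 7.4.2 already requires verification before randomisation. The cost is wording only, with 148/164 unchanged. The small downside is that a few ineligible subjects remain in ITT and may slightly shift the observed rates; the per-protocol analysis shows the result without them.
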